#### Contraction analysis

Whether subjects are in true labor or false labor, or perhaps transitioning into labor, will clinically be uncertain at the time of testing. The EMG data will be analyzed to predict the labor status, then the prediction will be correlated with the subject's outcome. Subjects who subsequently deliver within 24 hours will be considered to have been in labor. Those who deliver after 72 hours or more will be considered to be not-in-labor. Subjects who deliver between 24 and 72 hours will be considered to be transitioning into labor.

Endpoint 1.3 – Contraction analysis. Standard methods for EMG analysis of uterine signals utilizes the power of the EMG signal at each time point. The power values are then mathematically converted to mimic the time-dependent tracing of the Toco. In the PreTel analysis, up to 15 sensors will be distributed across the maternal abdomen to measure uEMG activity at each location. Each sensor will detect uEMG events as a function of time, but the events will not be scaled by power. Instead, the bioelectrical activity of each channel will be converted to an assessment of the presence or absence of a bioelectrical event at each time point and in each location. At each time point, events in all channels will be summed to yield a single time-dependent event tracing. This tracing will be mathematically converted to mimic the time-dependent tracing of the Toco. The PreTel Contraction Analysis software program will perform this analysis.

The PreTel Contraction Analysis will be compared against the Toco/IUPC tracing for sensitivity and specificity.

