## **2. STUDY DESIGN**

### **2.1. Overview**

This is an NIH SBIR feasibility and efficacy study. This study seeks to validate the reliability of the PreTel Regional Contraction uEMG/ECG Fetal Monitor in accurately determining contraction and the fetal heart rate. The study also seeks to validate the reliability with which the monitor is able to determine true labor contractions from false labor contractions. The study will achieve these goals by utilizing the PreTel Regional Contraction uEMG/ECG Fetal Monitor concurrently with standard fetal and uterine monitoring prior to and during labor.

Patients will be approached as they present for evaluation of labor in Triage and Labor and Delivery. After obtaining consent, we will have the subject sit, slightly reclining. We will place up to 15 EMG electrode pads over her abdomen, spanning most of the surface of the uterus, plus one ground electrode. The arrangement of the electrodes will be documented. If the patient consents to photo-documentation of the arrangement, then a de-identified photo of the sensor arrangement will be taken and stored electronically. The purpose of the image is to assess the

overall abdominal coverage of all EMG/ECG sensors and the placement of the legacy (traditional) monitors. The photograph may be taken before, during or after the completion of testing, so long as it accurately represents the locations of the area and pad sensors of the study device, and the Toco and Doppler of the legacy devices. Should significant adjustments of the study or legacy recording devices occur, such that the locations change, additional photographs may be taken to provide additional information of sensor locations at different times during testing. If the subject requests that a photograph not be taken, or if there is a technical reason that a photograph cannot be obtained, no photograph will be taken, and the subject will continue as a research subject (i.e. She will not be withdrawn from the study.) Failure to obtain an image will not be considered a breach of protocol and will not be reportable as such.

We will record multichannel EMG signals for 60 minutes for each subject. The subject will be eligible for compensation as outlined in section 10.1.

All health care management decision will be based on the standard obstetrical testing.

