#### 3.2. Inclusion and Exclusion Criteria

##### a) Inclusion Criteria:

- Age 18 or greater
- At least 30 weeks gestation
- English reading and speaking
- Female gender
- Singleton fetus
- Experiencing contractions and <3cm dilated
- Patients’ primary complaint or primary reason for seeking evaluation is uterine contractions and/or suspected labor.
- May be undergoing induction or augmentation of labor (Induction or augmentation refers to any mechanical or medical technique except artificial rupture of membranes (AROM). Subjects undergoing AROM alone, without other induction or augmentation techniques being used concurrently, will be included as a special category within spontaneous labor)
- May have clinical indications for internal monitoring (IUPC and/or FSE)
- Subjects may have intermittent fetal and uterine monitoring as a part of their overall birth plan; however for the 60 minutes of monitoring with EMG required for participation in the study, the subject must be willing to utilize continuous uterine and fetal monitoring.
- Subjects may be scheduled for induction of labor or Cesarean section delivery
- Patients must be able to review and sign informed consent to participate in the study.
- Trial of labor after cesarean section are eligible for participation
- Subjects with premature rupture of membranes in whom labor is augmented are eligible for inclusion in the study

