**4. SUBJECT IDENTIFICATION, RECRUITMENT AND CONSENT**

**4.1. Method Of Subject Identification And Recruitment**

Women who present for routine obstetrical care at URMC affiliated outpatient sites (i.e., Women's Health Practice, University OBGYN, Strong Perinatal Associates, and Special Care Clinic) and those women who present for evaluation of labor at URMC will be screened for participation. Screening will be performed by regular hospital staff (resident physicians, nurses, other obstetricians) or study coordinators screening subjects on L&D. Patients who meet criteria will be offered participation in the study. Not all patients who meet criteria will be offered the study. This will largely depend on the availability of research personnel (availability of a study coordinator to consent the subject) and the acuity on Labor and Delivery at the time of presentation.

BMI stratification will require us to enroll equal numbers of patients in each BMI category.

Subjects approached in the office by a study coordinator prior to their presentation in labor will be eligible to complete the consent prior to being in labor, presenting to URMC with suspected labor, presenting for an induction of labor or cesarean section. A note regarding their consent to participation in the study will be placed in their medical record in the Provider "Sticky Note" to inform hospital staff that the subject is in the study (see risk section). This notification will help to facilitate contacting the study coordinator at the time of the subjects' hospital admission.

All potential subjects will be told that we are investigating new methods to monitor the baby's heart beat and uterine contractions during labor, and that they will simultaneously receive standard-of-care clinical monitoring. Patients who refuse participation will receive the standard-of-care.

The date and time that the subject, or the subject's authorized representative, signs the informed consent form and a narrative of the issues discussed during the informed consent process will be documented in the subject's study case history. The Primary Investigator at URMC ([name]) will retain the original copy of the signed informed consent form and a copy will be provided to the subject or the subject's authorized representative.

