### 5. METHODS AND STUDY PROCEDURES

#### Monitoring before and during scheduled induction or Cesarean Section.

In many cases, patients present to labor and delivery for a clinically-indicated induction of labor or Cesarean Section. Following consent, study monitoring will be performed prior to initiation of labor induction or Cesarean Section. If the subject and the research personnel agree, study monitoring may be periodically discontinued, and restarted at a later time without requiring subject withdrawal.

For a scheduled induction, monitoring will occur when the patient is contracting and <3cm dilated. Recordings may be stopped and restarted multiple times for a single subject if needed.

For cesarean sections, the subject can undergo 60 minutes of EMG monitoring just prior to her planned cesarean delivery, if this would not otherwise delay delivery.

Triage patients:

Some patients (not scheduled for delivery), present to labor and delivery for evaluation of labor. They may perceive contractions, but may or may not be in active labor as defined by cervical change, or may or may not have experienced rupture of membranes.

Some patients present with rupture of membranes or a small abruption, in the preterm setting, and for these cases, the decision is usually made to not augment or induce labor. Alternatively, in the term setting, the decision to proceed with delivery via augmentation or induction for those noted conditions, is often made. For cases where the decision to not induce or augment labor is made, study monitoring can initially be performed for 60 minutes. In cases where the decision to deliver via induction, augmentation or expectant management is made, the protocol will be the same as in the sections describing monitoring before and during scheduled induction of labor.

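### Labor status is defined by time to delivery alone, so a woman recorded just before a planned cesarean is labeled in labor because of the surgical schedule, and section 14 has no rule for such recordings

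*Combined protocol and SAP*

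**What the plan says.** Section 14.2 (Contraction analysis) predicts labor status from the EMG and then compares the prediction with the subject's outcome. The outcome is time to delivery and nothing else. "Subjects who subsequently deliver within 24 hours will be considered to have been in labor"; "Subjects who deliver between 24 and 72 hours will be considered to be transitioning into labor"; and delivery at 72 hours or later counts as not in labor. Mode of delivery, whether delivery was planned, and cervical change play no part.

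On who is recorded, section 3.2(a) states that "Subjects may be scheduled for induction of labor or Cesarean section delivery". The same list requires every subject to be "Experiencing contractions and <3cm dilated" and requires that the "primary complaint or primary reason for seeking evaluation is uterine contractions and/or suspected labor". For cesareans, section 5 says that "the subject can undergo 60 minutes of EMG monitoring just prior to her planned cesarean delivery", provided delivery is not delayed. For scheduled inductions, section 5 repeats the contracting and under-3-cm condition.

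The label matters because section 2.1 sets out to validate how reliably "the monitor is able to determine true labor contractions from false labor contractions". Endpoint 1.4 gives the purpose as finding which SF values and trends go with labor and with its absence.

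**The concern.** A reference label should reflect the state that the device is meant to detect. Time to delivery is a reasonable proxy for labor when labor brings on the delivery. It is not when the operating schedule does. Take two women with the same contractions and the same cervix, one with a cesarean planned that day and one sent home who delivers more than 72 hours later. The rule calls the first in labor and the second not in labor, and the recording has no bearing on the difference.

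If women delivered by schedule have low SF and sit in the in-labor group, apparent sensitivity falls and the SF values learned as typical of labor are pulled down. Those values are what Endpoint 1.4 is meant to produce.

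**Working it through.** **1. Does any rule catch these recordings?** Section 14 contains no exclusion, stratum or alternative label for planned cesarean or induction. The case-by-case provision in section 2.1 covers missing data only. Section 14.1 assumes no patient subcategories, but that rests on uniform EMG signals in term women in active labor and does not concern how the outcome is assigned. Section 5 links labor to cervical change for triage patients, but section 14 does not use that criterion. So the time rule applies as written.

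**2. Which class do they fall in?** Recording takes place just before the operation, so nearly all fall in the under-24-hour class. The 24-to-72-hour class is a minor case.

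**3. Which analyses use the label?** Only SF against labor status. Endpoints 1.1 to 1.3, Endpoints 2.1 to 2.4b, the maternal heart rate analyses and the comparison of SF with IUPC peak pressure do not.

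**4. How large could the effect be?** The plan gives no figure for this point, so there is none to reproduce. The sample size of 23 in section 14.1 is not tied to the labor label, and I derive no power loss from it. What follows is an illustration.

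Inputs, all assumed here:
- 25 recordings labeled in labor.
- SF-positive rates of 0.75 in labor and 0.25 not in labor. The values are borrowed from the expected ratios in section 14.1, which does not present them as SF-positive rates.
- k affected recordings with SF-positive rate r, where r = 0.25 if none is truly in labor, 0.50 if half are, and 0.75 if all are.

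Formulas: sensitivity = (1 − k/25) × 0.75 + (k/25) × r; odds ratio = [sensitivity/(1 − sensitivity)] ÷ (0.25/0.75).

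| k | none in labor: sensitivity, odds ratio | half in labor: sensitivity, odds ratio | all in labor: sensitivity, odds ratio |
|---|---|---|---|
| 0 | 0.75, 9.0 | 0.75, 9.0 | 0.75, 9.0 |
| 1 | 0.73, 8.1 | 0.74, 8.5 | 0.75, 9.0 |
| 2 | 0.71, 7.3 | 0.73, 8.1 | 0.75, 9.0 |
| 3 | 0.69, 6.7 | 0.72, 7.7 | 0.75, 9.0 |
| 5 | 0.65, 5.6 | 0.70, 7.0 | 0.75, 9.0 |

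Example, k = 5 and none in labor: 0.8 × 0.75 + 0.2 × 0.25 = 0.65, and (0.65/0.35) × 3 = 5.6. The shift per affected recording is (0.75 − r)/25, that is 0.02, 0.01 or 0.

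**5. What precision is lost by setting recordings aside?** The 95% Wilson half-width around 0.75 is [1.96/(1 + 1.96²/n)] × √(0.75 × 0.25/n + 1.96²/(4n²)). It is 0.162 at n = 25, 0.178 at n = 20 and about 0.20 at n = 15.

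**The case against.** The strongest reply is that section 3.2(a) already limits the problem. Being scheduled for cesarean does not waive the requirements for contractions and a labor-type complaint. A woman attending only for surgery, without contractions, is not eligible. The affected group is therefore women with a planned cesarean who also present contracting, and some of them may truly be in labor. This stands, and it rules out two stronger readings.
- A reader might infer that the label says nothing about labor in these women. That goes too far: the label is non-specific, but it is not always wrong.
- A reader might infer from section 4.1, which lists women "presenting for an induction of labor or cesarean section" apart from those with suspected labor, that non-contracting women are recorded. That sentence concerns when consent may be signed and does not widen eligibility.

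The reply does not rescue the label. Section 14.2 itself accepts that labor status is clinically unclear when the recording is made. Contractions below 3 cm are exactly where true and false labor have to be told apart, so meeting the entry criteria cannot confirm that a woman was in labor.

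It can also be said that this is a pilot study, that Endpoint 1.4 works with averages and trends rather than a binary SF test, and that 0.65 lies inside the 95% Wilson interval around 0.75 at n = 25 (about 0.56 to 0.88). All of this is fair, and it is why the table is only an illustration. It bears on the size of the effect and leaves the gap in the rule as it is.

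**Conclusion.** The point holds and should be fixed. On the text it is certain: the rule uses time to delivery alone, women can be recorded just before a planned cesarean, and section 14 does not provide for them. Deliveries brought on by induction, whether scheduled or decided in triage, are affected in part, because the decision to induce influences the time to delivery.

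The size is unknown and may be small. It depends on the number of planned cesareans and on the share of those women truly in labor, and the documents give neither. Under the stated assumptions the loss is 0 to 0.02 in apparent sensitivity per affected recording, and there is no bias if all of them are in labor. A reader might infer that the contraction-detection or heart-rate results are compromised as well. They are not, because they do not use the label.

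**What to change.** Add to section 14.2, for the SF-versus-labor-status analysis only:

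1. Set aside from the primary analysis, and report separately, recordings from women scheduled for cesarean at the time of recording who then deliver by that cesarean within 72 hours. Identify them by scheduled status and by mode and time of delivery. No judgment is needed on whether labor had begun.
2. Report as a separate stratum recordings made before an induction, scheduled or decided in triage, that leads to delivery within 72 hours.
3. Keep women who deliver at 72 hours or later as not in labor, and keep spontaneous labor that was later augmented.
4. Give an all-subject sensitivity analysis under the current time rule.

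Record at enrollment whether delivery is scheduled (none, cesarean or induction), if the case report form does not already capture it. The form itself is not in the text available. The items listed in section 2.1 merge induced with augmented labor and do not separate planned from unplanned cesarean.

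The cost is some wording and possibly one form entry. Some true-labor recordings will be set aside, and precision falls in this one analysis: from an assumed 25, the half-width rises from 0.162 to 0.178 if 5 leave, and to about 0.20 if 10 leave. All subjects stay in every other endpoint.

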#### Endpoint 1.4 – Synchronization Factor.

Prior to conversion to the time-dependent tracing that mimics the Toco, the summed time-dependent event tracing will be mathematically converted to the fraction of sensors showing simultaneous, or synchronized activity. This will be the “Synchronization factor”, SF. The maximal SF for each contraction will be stored and reported as the SF associated with that contraction. We will compare the SF with the peak strength (in mmHg) as measured by the IUPC, anticipating that high values of SF are associated with a strong contraction, and consistently high SF values in sequential contractions are indicative of true labor.

For example, if half the sensors are simultaneously active during a given contraction, then  $SF = 0.50$  for that contraction. For the next contraction, it is possible that  $SF = 0.25$ . Over time, if the average SF trends to  $SF < 0.25$ , the subject will be predicted to be not in-labor. Alternately, if SF trends to  $SF > 0.75$ , those subjects will be predicted to be in-labor. The purpose of this research is to quantify this relationship, and determine the specific values and trends of SF that are associated with labor and not-in-labor, and in both pre-term and term pregnancies.

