## **1. PURPOSE OF THE STUDY AND BACKGROUND**

### **1.1. Purpose of the study**

This research is a traditional feasibility study designed to clinically characterize PreTel's uterine EMG/ECG fetal monitor for regional contraction detection and synchronization in laboring and non-laboring patients.

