### **14. DATA ANALYSIS AND MONITORING**

#### **14.1. Sample Size Determination**

This project is a pilot study to assess the reliability of uEMG compared to tocodynamometry for recording uterine contractions. Patient-to-patient variations include body habitus, uterine size, contraction strength and the amount of cervical dilation. We are not capable of controlling for all clinical variables, but assume that term patients carrying one baby in active labor will have contractions that are nearly uniform in producing uterine EMG signals. Thus, for these analyses, we assume that there are no subcategories of patient variables in the study population.

A sample size of 23 was determined using Odds Ratio statistics, assuming a 50% discrimination is clinically the minimum acceptable,  $\alpha=0.05$ ;  $\beta=0.8$ ; expected .75/.25 ratios. For each patient of 60 minutes of recording, we anticipate a minimum of 10 contractions could be observed. On average, we assume 10 contractions, for 23 patients, or 230 contractions.

However, to accommodate for patients who are enrolled in the study but who are subsequently excluded because of inability to complete the monitoring session, we will plan to recruit up to 50 patients.

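### The SF labor cut-offs are to be found in one cohort with no locked rule or internal validation stated, so accuracy quoted at them without correction could be too high and could not support validation

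*Combined protocol and SAP*

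**What the plan says.** Section 14.2, Endpoint 1.4, defines SF as the fraction of sensors active together and stores its maximum for each contraction. Values below 0.25 (not in labor) and above 0.75 (in labor) appear inside a worked example that turns on the phrase "Over time, if the average SF trends to". The plan does not define what counts as a trend and gives no prediction for 0.25 to 0.75. The section then states the aim: "The purpose of this research is to quantify this relationship, and determine the specific values and trends of SF that are associated with labor". The same sentence extends this to subjects who are not laboring, before term as well as at term.

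The comparison with outcome is in Section 14.2, Contraction analysis: "The EMG data will be analyzed to predict the labor status, then the prediction will be correlated with the" outcome of that subject. The reference classes are set by time to delivery: "Subjects who subsequently deliver within 24 hours will be considered to have been in labor"; 72 hours or more is not in labor, and the interval between is transitional.

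Section 2.1 states the ambition: "The study also seeks to validate the reliability with which the monitor is able to determine true labor contractions from false labor contractions". Sections 1.1 and 14.1 are more modest: "This research is a traditional feasibility study designed to clinically characterize" the monitor, and "This project is a pilot study to assess the reliability of uEMG compared to tocodynamometry for recording uterine contractions".

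Sections 3.1 and 14.1 describe one cohort of up to 50, with a calculated size of 23. Section 3.2 admits subjects scheduled for induction or cesarean, and Section 5 allows recording just before a planned cesarean.

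**The concern.** A rule chosen because it separates a set of subjects well will usually look better in that set than in new subjects. The plan states no safeguard against this for SF: no rule fixed before outcomes are seen, no held-out subjects, no cross-validation or bootstrap. The run-in wording in Section 14.2 and the training wording under Endpoint 2.4a concern contraction-detection sensitivity. Endpoints 2.1 to 2.4b do not retest SF as a predictor of labor.

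SF is the study's evidence on true versus false labor, so an inflated figure would overstate its main new claim. Care decisions rest on standard monitoring, so the harm would be to the conclusion and not to the subjects.

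A second, separate weakness lies in the reference standard. A subject recorded shortly before a planned cesarean delivers within 24 hours because of the schedule, yet the stated rule classes her as in labor. Internal validation would not remove that error.

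**Working it through.** **1. The plan's own size.** Section 14.1 gives 23 from a 50% minimum, .75/.25, α = 0.05 and β = 0.8 (read here as power). Sidedness is not stated. A one-sided, one-sample test of 0.75 against 0.50 reproduces it:

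n = [(1.645 × 0.5 + 0.842 × √(0.75 × 0.25)) / 0.25]² = 22.5, rounded up to 23.

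This makes no allowance for choosing a cut-off on the same data. Below, 23 and 50 serve only as plausible sample sizes.

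**2. Assumptions.** The documents give no class split and no SF distribution. I assume one normal SF summary per subject, two classes (labor, not in labor) and one cut-off. The class means are 0 SD apart (uninformative SF) or 2 × z(0.75) = 1.349 SD apart (a midpoint cut-off is then truly 75% accurate). Balanced accuracy is (sensitivity + specificity) / 2. Apparent accuracy is measured on the subjects used to choose the cut-off. True accuracy is that of the chosen cut-off in new subjects. There were 6,000 simulations per cell.

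**3. Cut-off chosen to maximize balanced accuracy (apparent v true).**

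| Labor v not | Uninformative SF | Excess | 75% case | Excess |
|---|---|---|---|---|
| 12 v 11 | 0.613 v 0.500 | 0.113 | 0.815 v 0.729 | 0.086 |
| 18 v 5 | 0.635 v 0.500 | 0.135 | 0.832 v 0.723 | 0.109 |
| 20 v 3 | 0.663 v 0.500 | 0.163 | 0.854 v 0.716 | 0.138 |
| 25 v 25 | 0.579 v 0.500 | 0.079 | 0.792 v 0.736 | 0.056 |
| 40 v 10 | 0.599 v 0.500 | 0.099 | 0.806 v 0.732 | 0.074 |

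The range is about 6 to 16 points. Setting aside the 24-to-72-hour group would shrink N and raise these figures. If raw accuracy is maximized and reported instead, with unequal classes, the excess is smaller: 2 to 4 points (uninformative) and 4 to 7 points (75% case).

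**4. Cut-off set at the midpoint of the two observed class means.** This is also derived from the same subjects.
- Uninformative SF: 0.499 v 0.500 (12 v 11), 0.500 v 0.500 (20 v 3 and 25 v 25). No excess.
- 75% case: 0.755 v 0.746 (12 v 11), 0.760 v 0.743 (18 v 5), 0.763 v 0.741 (20 v 3), 0.753 v 0.748 (25 v 25), 0.753 v 0.747 (40 v 10). Excess about 0.5 to 2 points.

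**5. Midpoint cut-off fixed in advance.** Apparent accuracy equals true accuracy: 0.50 and 0.75.

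**6. What correction achieves.** For the maximizing cut-off, five-times-repeated stratified 5-fold cross-validation is nearly unbiased: at 12 v 11, 0.498 v 0.500 and 0.729 v 0.728. It is imprecise, with SD 0.09 to 0.12 at N = 23 and 0.06 to 0.08 at N = 50. At 12 v 11 in the 75% case, leave-one-out gave 0.749 and a bootstrap correction 0.767, against a true 0.729, so about 2 to 4 points remained.

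**7. Cut-off-free measure.** A separation of 1.349 SD gives AUC A = Φ(1.349/√2) = 0.83. The Hanley-McNeil variance is [A(1−A) + (n₁−1)(Q₁−A²) + (n₀−1)(Q₂−A²)] / (n₁n₀), with Q₁ = A/(2−A) = 0.709 and Q₂ = 2A²/(1+A) = 0.753. At 12 v 11 the 95% half-width is 0.171; at 25 v 25 it is 0.115.

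**8. Scheduled deliveries.** Suppose a share f of the within-24-hour class has SF like subjects not in labor. The expected AUC is (1−f) × 0.83 + f × 0.5: 0.80 at f = 10%, 0.76 at 20%, 0.70 at 40%. These shares are assumptions; the documents give none. This error lowers apparent discrimination, whereas cut-off selection can raise it.

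**The case against.** The best defense is that the plan promises little for SF. It calls itself a feasibility study and a pilot, openly says that it will find the cut-offs, and sets no SF accuracy statistic or success bar. That stands: deriving cut-offs here is proper.

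Three stronger readings are tempting, and the documents support none of them.
- A reader might infer that derived cut-offs will be scored on the same subjects. The plan says only that a prediction will be correlated with outcome. The sensitivity and specificity in that section refer to contraction detection against Toco/IUPC. The bias is therefore conditional on what is reported.
- A reader might infer that any same-sample cut-off makes an uninformative SF look better than chance. Step 4 shows otherwise. The large figures need a search that maximizes the reported metric, and the plan names no such search.
- A reader might take 0.25/0.75 as a pre-set rule ready to be validated. The values sit in an example, with the trend undefined and the middle range unassigned.

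Two further objections have force. Cross-validated estimates at N = 23 are about as imprecise as the bias is large, which favors an exploratory label over reliance on correction alone. On scheduled deliveries, Section 3.2 also requires contractions, and contractions or suspected labor as the reason for evaluation. Some scheduled subjects may therefore truly be in labor, and the mislabeled share may be small.

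**Conclusion.** The point holds in conditional form. SF values and trends are to be determined from one cohort, the EMG prediction is set against the same subjects' outcomes, and nothing is stated that would keep an accuracy figure honest. Such a figure, uncorrected, can be too high and cannot support the validation aim in Section 2.1. On the assumptions shown, the excess in balanced accuracy is about 6 to 16 points for a maximizing cut-off, 0 to 2 points for a midpoint of class means, and nil for a cut-off fixed in advance. Which applies cannot be told from the plan.

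The scheduled-delivery problem follows from the stated rule and is separate; its size is unknown. Severity is minor to moderate: the study is a pilot, no SF decision rule depends on the figure, and care is unaffected.

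**What to change.** 1. In Endpoint 1.4, label SF cut-offs and trend rules derived in this study as exploratory. In Section 2.1, remove or limit the validation wording for labor discrimination, unless one complete SF rule (summary measure, cut-offs, handling of 0.25 to 0.75) is fixed before outcomes are seen.
2. Report any accuracy at derived cut-offs with internal validation at subject level. It should repeat the whole selection step, keep all sessions of a subject together (Section 5 allows several), and carry confidence intervals. Add an AUC with 95% CI for delivery within 24 hours versus 72 hours or more. Report sparse preterm or term subsets descriptively.
3. Report the SF-labor results with and without subjects whose delivery timing was set by a scheduled cesarean or induction.

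The SF summary, resampling scheme and minimum subset size are for the sponsor's statistician to choose; the summary should still allow the trends that Endpoint 1.4 sets out to study.

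Cost: some SAP wording, a short script and possibly one CRF tick box for scheduled delivery (onset of labor and mode of delivery are already collected). No added subjects or procedures are needed. The reported accuracy may be less favorable, with wide intervals.
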